1.10. Compliance

This study will be conducted in compliance with this protocol, Good Clinical Practice (GCP), and all applicable regulatory requirements.

2. OBJECTIVES

The primary objective of this study is:

- To evaluate the short-term antiviral potency of a regimen containing GS-9131 at doses up to 180 mg compared to placebo-to-match (PTM) GS-9131, each administered once daily with the existing failing ARV regimen, as demonstrated by the proportion of subjects with HIV-1 RNA decreases from baseline exceeding $0.5 \log_{10}$ through 14 days of therapy in HIV-1 positive, ARV TE adult subjects with nucleos(t)ide resistant virus.

The secondary objectives of this study are:

Part 1

- To evaluate the efficacy of GS-9131 functional monotherapy as determined by the change from baseline in \log_{10} HIV-1 RNA at Day 11 (Sentinel Cohort 1) or Day 15 (Sentinel Cohort 2 and Randomized Cohort)..

Part 2

- To evaluate the safety and efficacy of a regimen containing GS-9131 (60 mg) + bicitgravir (BIC) + darunavir (DRV) + ritonavir (RTV) through 24 weeks of treatment in subjects from Sentinel Cohort 1 who switched from a failing regimen.
- To evaluate the safety and efficacy of a regimen containing GS-9131 + bicitgravir (BIC) + tenofovir alafenamide (TAF) through 24 weeks of treatment in subjects from Sentinel Cohort 2 and Randomized Cohort who switched from a failing regimen.
- To characterize the pharmacokinetics (PK) of GS-9131 in treatment-experienced patients.
- To evaluate the number of subjects with treatment-emergent nucleos(t)ide reverse transcriptase inhibitor (NRTI), protease inhibitor (PI), and integrase strand-transfer inhibitor (INSTI) mutations at the time of virologic failure.

3. STUDY DESIGN

3.1. Endpoints

The primary endpoint of this study is:

- The proportion of subjects with plasma HIV-1 RNA decreases from baseline exceeding 0.5 log₁₀ at Day 15 in the Randomized Cohort in Part 1.

The secondary endpoints of this study are:

Part 1

- The change from baseline in plasma log₁₀ HIV-1 RNA (copies/mL) at Day 11 (Sentinel Cohort 1) and Day 15 (Sentinel Cohort 2 and Randomized Cohort) in Part 1.

Part 2

- The proportion of subjects with plasma HIV-1 RNA < 50 copies/mL as defined by the US FDA Snapshot algorithm at Week 24.
- The change from Part 2 baseline in plasma log₁₀ HIV-1 RNA (copies/mL) at Week 24.
- The change from Part 2 baseline in CD4 cell count (cells/μL) at Week 24.
- Number of subjects with treatment-emergent NRTI, PI, and INSTI mutations at the time of virologic failure.

3.2. Study Design

This protocol describes a partially-randomized, partially-blinded, multicenter, two-part study. Part 1 consists of three cohorts: Two Sentinel Cohorts followed by a Randomized Cohort.

The Sentinel Cohort 1 is an open-label cohort that will enroll 10 HIV-1 positive subjects to receive GS-9131 60 mg plus their current failing regimen for 10 days. Subjects who achieve > 0.5 log decrease at Day 11 will initiate a regimen of GS-9131 (60 mg) + BIC (30 mg) + DRV (800 mg) + RTV (100 mg) for 24 weeks.

The Sentinel Cohort 2 is an open-label cohort that will enroll up to 10 HIV-1 positive subjects to receive GS-9131 180 mg plus their current failing regimen for 14 days. Subjects who achieve > 0.5 log decrease at Day 15 will proceed to Part 2 in which they will initiate a regimen of GS-9131 + BIC (75 mg) + TAF (25 mg) for 24 weeks.

The Randomized Cohort of the study is double-blinded, randomized, and will assess the efficacy of GS-9131 doses up to 180 mg versus placebo in up to 48 HIV-1 infected, TE subjects who are failing their current ARV regimen. Subjects who achieve > 0.5 log decrease at Day 15 will proceed to Part 2 in which they will initiate a regimen of GS-9131 + BIC (75 mg) + TAF (25 mg) for 24 weeks. Subjects who achieve > 0.5 log decrease at Day 15 will proceed to Part 2 in which they will initiate a regimen of GS-9131 + BIC (75 mg) + TAF (25 mg) for 24 weeks.

3.3. Study Treatments

Subjects who provide written consent and meet all eligibility criteria will be allocated to one of the following treatment groups as follows:

Part 1: GS-9131 Functional Monotherapy

Part 1 consists of 3 cohorts:

Sentinel Cohort 1:

Approximately 10 TE viremic HIV-1 subjects will be enrolled to receive open-label GS-9131 60 mg in addition to their current failing ARV regimen.

Sentinel Cohort 2:

Up to 10 TE viremic HIV-1 subjects will be enrolled to receive open-label GS-9131 180 mg in addition to their current failing ARV regimen.

Randomized Cohort:

Up to 48 subjects failing their current ARV regimen will be randomized to GS-9131 (up to 180 mg) or PTM. These drugs will be added to their failing regimen for 14 days described below. Doses and number of cohorts will be determined by data from Sentinel Cohort 2:

- Treatment Arms A-C: GS-9131 up to 180 mg once daily + current failing ART regimen (n=12 per cohort)
- Treatment Arm D: PTM GS-9131 + current failing ART regimen (n=12)

Randomization will be stratified by HIV-1 RNA level ($\leq 100,000$ copies/mL and $> 100,000$ copies/mL) at screening.

Subjects enrolled in Part 1 who do not successfully complete the study drug doses in Part 1 will not continue onto Part 2 of the study.

Subjects enrolled in Part 1 who do not show a reduction in HIV RNA $> 0.5 \log_{10}$ from baseline to Part 2 Day 1 will have an Early Study Drug Discontinuation (ESDD) visit within 72 hours of laboratory results being available. They will have study medications discontinued and will not continue to Part 2.

Part 2 (Sentinel Cohort 1): GS-9131 + BIC + DRV+ RTV Regimen

In Part 2, subjects in Sentinel Cohort 1 will start a regimen consisting of GS-9131 (60 mg) + BIC (30 mg) + DRV+RTV (800 mg/100 mg) for 24 weeks. CCI

Part 2: GS-9131 + BIC + TAF Regimen (Subjects in Sentinel Cohort 2 and Randomized Cohorts)

All subjects who successfully complete all study drug doses in Sentinel Cohort 2 and the Randomized Cohorts will discontinue study drug from Part 1 on Day 15. To continue to Part 2, subjects must have a $> 0.5 \log_{10}$ decline in plasma HIV-1 RNA from their pre-GS-9131 baseline in the 14 days of functional monotherapy. Since this result will not be immediately available at the completion of Part 1, all subjects completing Part 1 will continue on their failing regimen until results are available. Results will be available no later than 9 days after completion of Part 1. Subjects who meet criteria will proceed to Day 1 of Part 2. Any subjects in the Sentinel Cohort, and Treatment Arms A, B and C who do not meet the criterion for $> 0.5 \log_{10}$ decline in plasma HIV-1 RNA from their pre-GS-9131 baseline will not continue to Part 2. All subjects in Treatment Arm D will be eligible to continue to Part 2. In Part 2, subjects from the Sentinel Cohort 2 and the Randomized Cohort will start a regimen consisting of GS-9131 (up to 180 mg) + BIC (75 mg) + TAF (25 mg) as described below.

- Treatment Arms A-C: GS-9131 (up to 180 mg)+ BIC + TAF
- Sentinel Cohort 2 and Treatment Arm D: GS-9131 180 mg + BIC + TAF

At Week 8, subjects who have plasma HIV-1 RNA < 200 copies/mL or who have an HIV-1 RNA ≥ 200 copies/mL and a reduction in HIV-1 RNA $> 1 \log_{10}$ from baseline at any study visit will continue study medications.

Subjects who have a confirmed sub-optimal virologic response at Week 8 defined as plasma HIV-1 RNA ≥ 200 copies/mL and reduction in HIV-1 RNA $\leq 1 \log_{10}$ from baseline at all study visits up to Week 12 may be discontinued from the study and further optimization of their ARV regimen if feasible will be done by the Investigator. Subjects meeting criteria for sub-optimal virologic response as further defined in Section 6.10.1 will be contacted for an ESDD visit and discontinued from the study within 72 hours of results being available.

Subjects with protocol-defined virologic failure and evidence of treatment emergent resistance to any component of their regimen at any time will be discontinued from the study drug and treated with an ARV regimen chosen by the Investigator. For additional information, please reference ESDD (Section 6.4.1).

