- b. Subjects on GS-9131 (including all subjects in the Sentinel Cohort and those on Treatment Arm A, B, and C of the Randomized Cohort) who have a ≤ 0.5 log₁₀ decline in HIV-1 RNA will be discontinued from the study and will not be eligible to continue into Part 2 of the study. The Sponsor will notify the site regarding subject enrollment criteria for Part 2 prior to the visit.
- c. Subjects who complete Day 14 of Part 1 (from either the Sentinel Cohort or Treatment Arm D of the Randomized Cohort) will discontinue their GS-9131 or PTM but remain on their failing ARV regimen until the site is notified of the subject's eligibility to proceed to Part 2.
- d. [REDACTED]
- e. In Part 1 Randomized Cohort 2, Treatment Arms A-C will be assigned up to three dose levels of GS-9131, up to 180 mg. The GS-9131 dose for Treatment Arm A-C will be determined following review of the Sentinel Cohort 2. Doses of GS-9131 for subjects in the randomized cohorts A-C will correspond to the respective dose selected in Part 2. All subjects will continue a regimen of GS-9131+BIC+TAF at the assigned GS-9131 until determination of the optimal GS-9131 dose following Part 1 data review of the randomized cohort.

CCI

[REDACTED]

CCI

[REDACTED]

[REDACTED]

CCI [Redacted]

[Redacted]

[Redacted]

[Redacted]

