5.1.1. Procedures for Breaking Treatment Codes

In the event of a medical emergency where breaking the blind is required to provide medical care to the subject, the investigator may obtain treatment assignment directly from the IWRS system for that subject. Gilead recommends but does not require that the investigator contact the Gilead medical monitor before breaking the blind. Treatment assignment should remain blinded unless that knowledge is necessary to determine emergency medical care for the subject. The rationale for unblinding must be clearly explained in source documentation and on the electronic case report form (eCRF), along with the date on which the treatment assignment was obtained. The investigator is requested to contact the Gilead medical monitor promptly in the event of any treatment unblinding.

Blinding of study treatment is critical to the integrity of this clinical trial and therefore, if a subject's treatment assignment is disclosed to the investigator, the subject will have study treatment discontinued. All subjects will be followed until study completion unless consent to do so is specifically withdrawn by the subject.

Gilead Pharmacovigilance and Epidemiology (PVE) may independently unblind cases for expedited reporting of suspected unexpected serious adverse reactions (SUSARs).

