- Administration of study drug by DOT. Study drug, as well as other ARVs, will be administered by DOT once daily. Any additional doses of ARVs, other than GS-9131, that cannot be administered at the same time will be documented by the subject in a dosing diary provided for the study. Study drug should be administered at approximately the same time each day.

6.3.2. Part 2

All subjects must complete Part 1 prior to initiating any Part 2 Day 1 Visit procedures. Before proceeding into Part 2, subjects who have completed Day 14 of Part 1 will discontinue GS-9131 or PTM but remain on their failing regimen until the site is notified of the subject's eligibility to proceed to Part 2. This period shall be no longer than 14 days (for Sentinel Cohort 1)/9 days (Sentinel Cohort 2 and Randomized Cohort), while awaiting HIV-1 RNA results and the authorization to proceed from Gilead.

Once notified of their eligibility into Part 2 of the study, the subject will discontinue their failing regimen before initiating any Part 2 Day 1 study procedures. Subjects who received GS-9131 (including all subjects in the Sentinel Cohort 2 and those on Treatment Arms A-C of the Randomized Cohort) and had a $\leq 0.5 \log_{10}$ decline in HIV-1 RNA will be discontinued from the study early and will have a 30 day visit following this visit.

In the event the plasma HIV-1 RNA test results performed by the central laboratory are delayed, a subject may still proceed to Part 2 of the study if the test results from the local laboratory show a reduction in plasma HIV-1 RNA $> 0.5 \log_{10}$ compared to pre-GS-9131 baseline during the 14 days of GS-9131 functional monotherapy in Part 1 of the study. If the local laboratory test results do not show a reduction in plasma HIV-1 RNA $> 0.5 \log_{10}$ and the central laboratory test results are not received ≤ 9 days from completion of Day 15 of Part 1, the subject will be discontinued from the study and will be required to return to the clinic 30 days after the last dose of study drug for the 30-Day Follow-Up Visit. After a subject has terminated their participation in the study, long-term care for the subject will remain the responsibility of their primary treating physician, who will have access to the subject's clinical information, including plasma HIV-1 RNA viral load and HIV-1 genotype testing results.

Part 2 Day 1 Treatment Assessments

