8.10. Data Monitoring Committee

An external Independent Data Monitoring Committee (IDMC) will review the progress, efficacy, and safety data of this study while the study is ongoing. The committee will convene after approximately 50% of subjects enrolled in Part 2 complete Week 12 of the study. However, Gilead will defer to the IDMC for any decision to convene earlier or more frequently. The IDMC will examine the safety results of the trial and also focus on logistical issues such as accrual, retention, quality of clinical and laboratory data, and implications of results of external studies. Blinding will be preserved for Part 1 during the conduct of the study and access to unblinded data will be limited to designated parties.

No formal stopping rules will be used by the IDMC for safety outcomes. Rather, a clinical assessment will be made to determine if the nature, frequency, and severity of adverse events associated with a study regimen warrant the early termination of the study in the best interest of the participants.

An analysis for the Week 12 IDMC meeting will be conducted after approximately 50% of subjects enrolled in Part 2 complete Week 12 of the study.

Gilead does not have a prior intent to ask the IDMC to consider early termination of the study even if there is early evidence of favorable efficacy.

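### The arm-dependent Part 2 entry rule lets a site tell active from placebo for every Part 1 non-responder, so the Part 1 blind promised in Protocol 8.10 ends at each subject's Part 2 notice

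*Protocol*

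**What the plan says.** **Blinding.** Protocol 3.2 states: "The Randomized Cohort of the study is double-blinded, randomized". Protocol 8.10 adds: "Blinding will be preserved for Part 1 during the conduct of the study and access to unblinded data will be limited to designated parties". That promise is not limited to Day 15.

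**Entry to Part 2.** Figure 3 note b (Protocol 3.4) says that GS-9131 subjects, including Arms A-C, with a decline of 0.5 log10 or less "will be discontinued from the study and will not be eligible to continue into Part 2 of the study". For placebo, Protocol 3.3 says "All subjects in Treatment Arm D will be eligible to continue to Part 2". The synopsis, the text of 3.4, 6.10.1 (which leaves the placebo group out of the suboptimal-response definition) and SAP 1.2 carry the same exemption. It applies to Arm D subjects who complete Part 1.

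**What the site learns.** Note b adds: "The Sponsor will notify the site regarding subject enrollment criteria for Part 2 prior to the visit". If central results are delayed, Protocol 6.3.2 says "a subject may still proceed to Part 2 of the study if the test results from the local laboratory show a reduction". No section withholds HIV-1 RNA from the site or plans an unblinding at Part 2 entry.

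**Unblinding rule.** Protocol 5.1.1 says that "if a subject's treatment assignment is disclosed to the investigator, the subject will have study treatment discontinued".

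**Text without the exemption.** Three places state the response criterion and do not except Arm D: the Randomized Cohort paragraph of 3.2, the paragraph in 3.3 on subjects without a reduction above 0.5 log10, and the delayed-results rule in 6.3.2.

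**The concern.** Two subjects with the same HIV-1 RNA result get opposite notices because of their arm. The notice therefore carries treatment information, and it reaches staff who are still assessing Part 1 safety.

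Adverse events are reported until 30 days after the last dose (Protocol 7.3.1). The investigator judges causality as yes or no (7.2.1). Relatedness also feeds the rule in 6.5.1 that convenes the IDMC for the Randomized Cohort. Once the arm is known, grading and causality in the placebo-controlled safety summaries are open to expectation. A reader who relied on 8.10 would believe otherwise.

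**Working it through.** **Inputs**

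- Allocation 1:1:1:1, 12 per arm, so 36 active and 12 placebo (synopsis; Protocol 8.9).
- Assumed response rates: 70% active, 8.3% placebo (Protocol 8.9; SAP 1.3).
- Sensitivity rate: 2 of 11 responders at 60 mg in Sentinel Cohort 1 (Protocol 1.2.3.3.1.1).
- Assumptions: all 48 complete Part 1, the site knows the HIV-1 RNA result, and the Arm D exemption applies.

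**The plan's own figure.** Exact enumeration of two binomials with n = 12, rates 70% and 8.3%, and a two-sided Fisher test at 0.05 gives power 0.859, against the stated 85%. The rates and arm sizes are therefore read as the plan intends. This power is not affected by the point made here.

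**What each combination reveals**

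| HIV-1 RNA decline | Notice | Arm implied |
|---|---|---|
| 0.5 log10 or less | proceed | placebo |
| 0.5 log10 or less | discontinue | active, dose not shown |
| above 0.5 log10 | proceed | not separated |

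**Expected number identified**

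- Active non-responders: 36 × (1 − 0.70) = 10.8.
- Placebo non-responders: 12 × (1 − 0.083) = 11.0.
- Total: 10.8 + 11.0 = 21.8, and 21.8 / 48 = 45%.

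**What the notice adds to the laboratory result.** Before the notice, a non-responder is placebo with probability 11.0 / 21.8 = 0.505, close to a coin toss. After it, the probability is 0 or 1. The best guess of active versus placebo is right for (11.0 + 25.2) / 48 = 75% of subjects from HIV-1 RNA alone, and for (21.8 + 25.2) / 48 = 98% with the notice. Here 25.2 = 36 × 0.70 is the expected number of active responders.

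**Sensitivity to the active response rate** (placebo held at 8.3%)

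| Active response | Active + placebo non-responders | Share of 48 |
|---|---|---|
| 70% | 10.8 + 11.0 = 21.8 | 45% |
| 50% | 18.0 + 11.0 = 29.0 | 60% |
| 30% | 25.2 + 11.0 = 36.2 | 75% |
| 2/11 | 29.5 + 11.0 = 40.5 | 84% |

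If the site did not know the HIV-1 RNA result, only the discontinued active subjects would be identified: 10.8 / 48 = 22.5%.

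**Timing.** The last Part 1 dose is on Day 14, so the 30-day window ends on Day 44. Results are due within 9 days of completing Part 1, that is by Day 15 + 9 = Day 24. A notice on Day 24 leaves 44 − 24 = 20 of the 30 days, about two-thirds. An earlier notice leaves more.

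**The case against.** Several points count against this concern.

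- **The primary endpoint is protected.** It is a Day 15 laboratory value drawn before the notice. A reader might infer that the efficacy comparison is biased. The documents do not support that for a subject's own endpoint.
- **Responders.** A reader might infer that nearly the whole cohort is unblinded, since a responder is active with probability 25.2 / (25.2 + 1.0) = 96%. That figure comes from the assumed response rates and exists before any notice. It is a probability, and the entry rule adds nothing to it.
- **The exemption is contradicted.** Under the text in 3.2, 3.3 and 6.3.2 that does not except Arm D, a discontinuation would not prove active treatment. This stands. It makes reconciliation necessary and does not remove the problem, because 3.3 elsewhere, the synopsis, 3.4, 6.10.1 and the SAP grant the exemption.
- **Section 5.1.1 concerns code-breaking.** A reader might infer that it flatly contradicts 3.3 by stopping treatment in the placebo non-responders whom 3.3 admits. That follows only if a certain inference counts as disclosure, which 5.1.1 does not say.
- **Section 8.10 is about data access.** Its second clause supports that reading, but the first clause is an unqualified statement that Part 1 blinding is preserved.
- **The exposed safety window is limited.** Adverse events are assessed daily through Day 15, and the safety outputs are summaries without between-arm tests. For the sentinel cohorts the SAP ends Part 1 data before the first Part 2 dose. The same cut in the Randomized Cohort would shorten the window for subjects who proceed, but not for active non-responders who are discontinued.

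**Conclusion.** The concern holds in a bounded form. Under the arm-dependent entry rule, a site that knows HIV-1 RNA can separate active from placebo for every non-responder among Part 1 completers: about 21.8 of 48 (45%) at the planned rates, 60% at 50% active response, and 84% at 2/11. The notice does not separate responders and does not show which of Arms A-C was assigned. The statement "Blinding will be preserved for Part 1 during the conduct of the study" is therefore not delivered at site level.

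The result rests on the Arm D exemption being operative and on the site having the HIV-1 RNA result. The second is not stated outright, but nothing masks the result and 6.3.2 allows local results to decide entry.

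What is at risk is Part 1 adverse event grading and causality recorded after the notice. No reported result is affected: SAP 2.4 and 6 record that the study was discontinued and that the Randomized Cohort produced no efficacy data. The point matters for the protocol as written and for any reuse of the design.

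**What to change.** 1. **Protocol 8.10:** state that the site-level Part 1 blind holds only until each subject's Part 2 notice.
2. **Protocol 6.3.2:** require onset, grade and causality of all Part 1 adverse events to date to be entered before the notice is released. Later changes stay possible, remain in the audit trail that 9.1.6 already describes, and are flagged as post-notice.
3. **Protocol 8.6 and the SAP:** keep the planned 30-day Part 1 safety tables and add one supplementary between-arm table limited to events assessed before the notice. Cutting every Part 1 safety table at the notice would discard data that 8.2.1.3 and 8.6 include.
4. **Reconcile the entry passages:** the text in 3.2, 3.3 and 6.3.2 that does not except Arm D must be brought into line with the synopsis, the rest of 3.3, 3.4 and 6.10.1. Section 5.1.1 should say whether an assignment inferred from the notice counts as disclosure. Which clinical rule should prevail is for the sponsor and investigators.

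The cost is a small data-entry step inside the 9-day wait, one extra table and a few sentences. The blinded window claimed becomes shorter, but it then matches what the design provides. These changes do not restore the blind after the notice; they record what was assessed before it.
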